### **10.3 Outcome Criteria**

#### **10.3.1 R61 Phase:**

Criteria	Goal (out of 5 subjects)
Device optimization and manufacturing in a clean/sterile manner	100%
Parent/CG reported ease of insertion; $\geq 5$ on Likert scale of 1-10	60%
Child able to tolerate device in place	60%
Child able to maintain device in place during sleep	60%
Parent/CG report of adherence based on diary	60%
Comfort rating $\geq 7$ on Likert scale of 1-10	60%

#### **10.3.2 Other Outcome Measures for the R61 Phase**

Secondary outcomes will determine change in sleep quality as well as other symptoms of OSA such as snoring and daytime sleepiness. Comparisons between baseline and 8-week outcomes for sleep quality and daytime sleepiness (measured continuously) will be made using paired t-tests with a p-value  $<0.05$  considered statistically significant. Exploratory analyses will determine changes in oxygen saturation nadir, sleep efficiency and possible improvement in sleep architecture such as increase in sleep efficiency, stage N3 and REM sleep. In addition, the insertion protocol will be optimized to make sure that it is safe, effective, and acceptable by parents/caregivers for ssNPA self-insertion. The current sizing protocol for physicians will also be optimized to effectively help physicians determine the proper length for ssNPA for each patient. These protocols will guide the larger clinical trial in R33 phase.

#### **10.3.3 R33 Phase**

We anticipate that use of the ssNPA will show clinically meaningful improvement (reduce the AHI by at least 50% and to a level  $<15$ ) in substantial percentage ( $>60\%$ ) of children with OSA and that the device will be able to be tolerated by greater than 60% of children and parents.

#### **10.3.4 Other Outcome Measures for the R33 Phase**

We expect that subjective sleep-related symptoms including impaired sleep quality, snoring, and daytime sleepiness, as well as quality of life for both parent and child will be improved.

### **10.4 Dropouts/Lost-to-Follow-up**

In order to achieve the 95% confidence and statistics specified above, we need a sample size of 5 patients. Thus, we will conservatively assume up to 20% dropout from the study, and to ensure that a total of 5 children have complete outcome data, we will enroll 7 children.

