Families will return to the clinic at weeks 2 and 4 to ensure optimal care and evaluate the device safety, tolerability, and acceptability. In between the clinic visits, regular contact will be made with families by the team, daily during the first week and weekly by the 2nd week (see Appendices H-K). During these calls, caregivers will report night to night witnessed apneas, improvement in daytime awareness, improvement in sleeping patterns of the patient, and any adverse events. Beside the two clinical visits at 2nd and 4th week, the number and frequency of extra visits will depend on: (1) the child's current threshold; and (2) how the child and family advance through each step of the desensitization protocol. The decision to hold on a particular step of the desensitization program will be based on whether the child's current level of anxiety or opposition is elevated. A recommendation to discontinue ssNPA treatment may be made if the child or family do not make progress with wearing the device in 2-4 weeks (depending on the number of visits during that time). Discontinuation of ssNPA therapy may occur after case consultation with other members of the study team to ensure that all strategies have been considered.

Evaluation of the device safety, tolerability, and acceptability will be assessed by a survey of patients and caregivers using a validated questionnaire with 10-point response scale (Appendix K). Mean and standard deviation scores as well as the percentage of those reporting satisfactory or better will be assessed. Device safety will be determined by adverse events

Table 3. Milestones for successful completion of the R61 phase

R61 Milestones	Goal (out of 5 subjects)
1. Device optimization and manufacturing in clean/sterile manner	100%
2. Parent report of ease of insertion; $\geq 5$ on Likert scale of 1-10	60% (3 of 5)
3. Child able to tolerate device in place	60% (3 of 5)
4. Child able to maintain device in place during sleep	60% (3 of 5)
5. Parent report of adherence based on diary	60% (3 of 5)
6. Comfort rating $\geq 6$ on Likert scale of 1-10	60% (3 of 5)

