## **10.0 DATA ANALYSIS AND STATISTICAL CONSIDERATIONS**

### **10.1 Sample Size**

The sample size will be 5 pediatric patients with HUAO for the R61 phase and 40 pediatric patients for the R33 phase.

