## **11.8 Summary of Phases**

### *11.8.1 R61 Phase:*

In the R61 Phase, we will recruit up to 5 children with hypotonic collapse aged between 3-21 years who have had a sleep study at the Sleep Disorders Laboratory for clinical purposes and were diagnosed with severe OSA (AHI>10). Families will be invited to participate in the study and the PI or trained otolaryngologist designee will explain the ssNPA as a novel treatment option for OSA. For those families who are willing to participate, consent and assent (where appropriate) will be obtained and several sleep and quality of life assessments will be completed. Drs [name] or [name] will then perform the device fitting and confirm the optimal anatomy position for each child. Families will be given information about strategies to help children become familiar with the device and will be provided with contact details of the study nurse who will be available to help families. After approximately 8 weeks, a sleep study will be conducted to quantify the change in AHI with the ssNPA in place. Subjective sleep questionnaires and the quality of life assessments will also be repeated. During this phase we will optimize the development of the ssNPA device as well as optimize the delivery of the desensitization protocol. At the end of the R61 phase we will be ideally positioned to launch a randomized trial of the ssNPA in the R33 phase.

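### R61 recruits up to 5 children in section 11.8.1 but enrols 7 in section 10.4, and the milestones scored out of 5 do not say which 5 count or how an early stopper is scored

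*Combined protocol and SAP*

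**What the plan says.** Three places in the combined protocol and SAP bear on how many children enter R61:

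- Section 10.1: "The sample size will be 5 pediatric patients with HUAO for the R61 phase".
- Section 11.8.1: "we will recruit up to 5 children with hypotonic collapse".
- Section 10.4: "we will conservatively assume up to 20% dropout from the study", and therefore "to ensure that a total of 5 children have complete outcome data, we will enroll 7 children".

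Success is defined in section 9.2 (Stage 2), Table 3, titled "Milestones for successful completion of the R61 phase", and again in section 10.3.1. Both tables express the goals relative to 5 subjects. One milestone concerns manufacturing. The other five are judged child by child: ease of insertion, tolerance ("Child able to tolerate device in place"), keeping the device in during sleep, diary adherence and comfort. Each has a goal of 60%, which Table 3 spells out as 3 of 5. Section 9.4 starts R33 recruitment once R61 has succeeded.

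Sections 9.2 and 9.5.1 let the team recommend stopping the device when there is no headway within 2-4 weeks. Neither says how such a child is then scored. The intent-to-treat cohort, the failure rule for tracheostomy and the reporting of dropouts appear only in section 10.2.2, for R33.

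**The concern.** The ceiling in section 11.8.1 and the enrolment in section 10.4 cannot both be followed. The discrepancy matters because the milestones keep a denominator of 5 while section 10.4 provides for two further children, so that 5 end up with full data. Nothing says whether the 5 are the first enrolled, all those fitted, or those who finish.

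R61's primary objective (section 4.1) is tolerability, safety, comfort and ease of use. A child who abandons the device because it cannot be worn is a negative result on that objective. If that child is treated as attrition and another takes the place, the milestone is measured in children already selected for tolerating the device, and the decision to begin a randomised trial rests on a figure that is too high.

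**Working it through.** **1. The plan's own figure.** Inputs from section 10.4: 5 children with data, 20% dropout. 5 / (1 − 0.20) = 6.25, rounded up to 7. The 7 reproduces. Section 10.2.1 gives a margin of 1.24 SD for a mean; t(0.975, 4 df) / √5 = 1.242, so the planning number of 5 means children with data.

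**2. Consistency of the counts.** Section 10.1 gives a sample size, which can mean the analysed number. R33 is handled in the same way: 40 in section 10.1, and 40 / 0.80 = 50 enrolled in section 10.1.1. Section 11.8.1 sets an upper limit on recruitment, and 7 exceeds it.

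**3. Could early stoppers lack milestone data?** The insertion and comfort milestones are on 1-10 scales. Among the forms shown, only Appendix M uses 1-10. Section 9.2 (Stage 3) gives it after the results of the sleep study, which itself follows acclimation. Appendices I, J and K use 1-5 items, although section 9.2 describes Appendix K as a 10-point form. A child who stops early could therefore lack the 1-10 ratings. Tolerance itself is asked on the 1-5 forms from day one.

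**4. Effect of the denominator.**
- 3 tolerators among 5 completers: 3/5 = 60%, goal met.
- The same 3 among 7 fitted: 3/7 = 42.9%, goal missed.
- 60% of 7 = 4.2, so 5 are needed; 5/7 = 71.4%. (4/7 = 57.1% falls short.)

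**5. Chance of meeting one milestone.** Exact binomial, P(X ≥ k) = Σ C(n, j) p^j (1 − p)^(n − j) for j from k to n. The true rates p are illustrative assumptions. Worked at p = 0.5:
- at least 3 of 5: (10 + 5 + 1) / 32 = 0.500
- at least 3 of 7: 1 − (1 + 7 + 21) / 128 = 0.773
- at least 5 of 7: (21 + 7 + 1) / 128 = 0.227

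| Scoring | p = 40% | p = 50% | p = 60% |
|---|---|---|---|
| 5 fitted, all counted, at least 3 | 31.7% | 50.0% | 68.3% |
| 7 fitted, up to 2 non-tolerators removed (at least 3 of 7) | 58.0% | 77.3% | 90.4% |
| 7 fitted, all counted, at least 5 | 9.6% | 22.7% | 42.0% |
| 7 fitted, all counted, at least 4 | 29.0% | 50.0% | 71.0% |

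**6. How extreme the second row is.** It lets up to two children be removed, all of them non-tolerators. Two of 7 is 28.6%, above the 20% allowance, which corresponds to 7 × 0.20 = 1.4 children leaving for any reason.

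**The case against.** Several stronger readings are tempting, and the documents do not support them.

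A reader might infer that section 10.1 also caps R61 at 5. It does not: it states a sample size, and the R33 numbers show the same habit of quoting the analysed target and inflating it elsewhere. Only section 11.8.1 conflicts with section 10.4.

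A reader might infer that the two extra children will probably be tolerability failures. Sections 9.2 and 9.5.1 concern stopping the device; leaving the study is a separate provision in section 9.5.2, open to any family at any time. A child who stops at week 2-4 would normally already have tolerance answers on the day-one, daily and weekly forms.

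A reader might infer that the plan intends to drop such children. No section says so. Section 10.3.1 gives the child-level goals only as 60%, so applying that to every fitted child is an equally available reading.

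It is also fair to say that R61 is descriptive (section 10.2.1) and that the R33 primary analysis is separately intent-to-treat, so the efficacy comparison is untouched.

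All of this narrows the point without removing it. The two enrolment statements still conflict, the denominator is still undefined, and the 1-10 ratings may still be missing for just those children who stopped.

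**Conclusion.** The point holds as an inconsistency combined with an undefined decision rule. Sections 10.4 and 11.8.1 disagree on R61 enrolment, and the child-level milestones do not define their denominator or the scoring of early stoppers. Under a completers reading, a true 3/7 (43%) can be reported as 3/5 (60%).

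The increase over a fixed 5 in the chance of meeting one milestone, from 32% / 50% / 68% to 58% / 77% / 90%, is an upper bound. It rests on assumed tolerability rates of 40% / 50% / 60% and on every removed child being a non-tolerator. It describes a single milestone and is not the probability that R61 as a whole succeeds, since Table 3 has six. The correction is worth making before R61 is scored because it concerns the threshold for starting a randomised trial.

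**What to change.** - Give one R61 enrolment number in sections 10.4 and 11.8.1, and say in section 10.1 whether 5 means enrolled or completers.
- In Table 3 and section 10.3.1, score each child-level milestone over all children in whom the device was placed. Count a child who stops early or lacks the data as not meeting it.
- Replace only children who leave before first placement.
- Either keep 3 of 5 with five fitted children, or, if 7 are fitted, restate the threshold for 7.

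This is wording about enrolment and scoring and touches no clinical rule. The price depends on the last choice. With 7 fitted, 5 of 7 is a good deal harder than 3 of 5: the pass chance is 10% / 23% / 42% at true rates of 40% / 50% / 60%, so a device with exactly 60% tolerability would miss more often than not. A threshold of 4 of 7 behaves much like 3 of 5 (29% / 50% / 71%), but it is 57% and would have to be stated openly as below the 60% goal. Keeping 3 of 5 fitted children is the lower-cost option. Its drawback is that, at 20% dropout, all five would have full data only 0.8^5 = 33% of the time, so the descriptive means may be less precise than section 10.2.1 states.

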## **11.0 ETHICAL AND REGULATORY CONSIDERATIONS**

This study will be conducted in accordance with FDA's Good Clinical Practice regulations.

### ***11.1 Informed Consent***

In accordance with the provision of 21 CFR Part 50, each caregiver or subject will provide written informed consent for participation in this study prior to the use of the investigational device.

The study will be explained to the prospective caregiver and subject by the investigator or his designee. The nature of the experimental product will be explained together with potential hazards of the treatment including any possible adverse reactions. The subject will be informed that he/she is free to terminate participation in the study for any reason. One copy of the signed consent form will be retained in the medical record, and one copy will be given to the subject.

### ***11.2 Institutional Review Board***

This protocol and the informed consent form will be approved initially and reviewed annually by the University of Michigan Institutional Review Board (IRB). Progress reports will be submitted at the completion of the study or at least once yearly, whichever comes first, to the IRB. Serious adverse events will be reported to the IRB and in accordance with applicable regulations for serious adverse events.

### ***11.3 Protection of Human Subjects***

#### ***11.3.1. Human Subjects Involvement and Characteristics***

This Human Subjects Research meets the definition of Clinical Research.

Human Use Board Approval: All procedures described for the proposed study will be approved by the University of Michigan Medical School Institutional Review Board (IRBMED).

The proposed study will involve recruitment of children with Hypotonic Upper Airway Obstruction (HUAO) and obstructive sleep apnea (OSA) aged 3-21 years. Children with HUAO will undergo a baseline sleep study (polysomnogram) to determine presence of OSA and thus eligibility. Subjective sleep measures and quality of life will also be assessed. Those with an apnea hypopnea index (AHI) of greater than 10 events per hour will be eligible to receive therapy with the self-supported nasopharyngeal airway. Families will be instructed on use of the ssNPA and will encouraged to use it for approximately 8 weeks when the child will undergo a repeat polysomnogram. Thus all children stand to benefit from this novel intervention. However, within the 2-month time period it is highly likely that these children will not yet receive the SoC treatments such as Positive Airway Pressure (PAP) (in our institution it is common for it to be six months from initial referral to PAP titration and approximately 8-10 weeks from the time of a baseline study to a PAP titration). Subjective sleep measures and quality of life assessments will occur for all subjects at the end of each 8-week period. Demographic and relevant medical information will be extracted from medical records. All subjects and their families will be notified that consent to participate is voluntary and can be withdrawn at any time. Written informed consent will be obtained from each parent and assent will be obtained from subjects where appropriate.

Recruitment will occur at practices of otolaryngologists, sleep medicine physicians, and pediatricians as well as via parent support groups. The investigators have worked in such interdisciplinary groups and their staff for almost 20 years to recruit pediatric subjects successfully, achieving targeted goals for three other NIH-funded R01 projects.

Prior to study enrollment, tours of the sleep laboratory will give subjects and families a preview of that environment and equipment used there, reduce any possible fears or anxieties, and give them a good understanding of study requirements in relation to family, school, and job commitments. Technicians experienced with children, including children with developmental disabilities, and anxieties of this age group will conduct sleep studies. One parent will stay with each child during overnight testing to reduce separation anxiety. Spacious pediatric sleep rooms are designed to include a separate bed for the parent. During sleep studies, a physician investigator will always be on call for any unexpected emergencies. Studies will be performed in the 12-bed Michael S. Aldrich Sleep Disorders Laboratory, Division of Sleep Medicine, where a 24-hour technical staff including pediatric and research technologist pods is well prepared to meet the needs of children and families who participate in research. Finally, every effort will be made to ensure, as in the investigators' past NIH-funded pediatric sleep protocols, that this research experience is fun, positive, and rewarding for each subject and family.

Problems with ssNPA use will be preempted in part by thorough education of parents, and children, about the purpose, potential benefits, and importance of nightly adherence. Participating families will be well educated about potential problems, and what to do about them, even before starting ssNPA therapy. The device has demonstrated initial safety and efficacy in a pilot group of 4 patients with severe OSA (apnea/hypopnea index, or AHI, as high as 114/hour). The NPA devices will have a series of sizes (lengths and silicone attachment sizes) available for otolaryngologist to choose. The otolaryngologist will then determine the optimal size for each child to achieve the best fitting and appropriately bypass the obstruction. This will minimize risk for discomfort or irritation. After ssNPA therapy is initiated, contact initially with study team members will occur daily during the first week of using the device and will continue during following weeks if needed and will provide multiple opportunities to detect and correct problems. Use of ssNPA on every night will be encouraged: parents and children will be educated about its importance.

### **11.3.2. Sources of Research Material.**

Clinical data will be obtained for research purposes. Data from polysomnography, ssNPA therapy, and questionnaires will be collected and stored as research data. Information from medical records will be extracted. Access to medical records will be requested from the University of Michigan IRBMed, mainly for any demographic data, medication lists, or other information that might be missing from study-specific forms, and not for collection of any of the main variables under study. Each of the investigators will have access to individually identifiable private information about human subjects. Individuals not on the investigative team will not have access to this information. Written data will be stored in locked cabinets, in locked offices, separate from keys that identify subject names. Electronic data will be stored on password-protected, regularly-backed-up server files and on external hard drives kept securely.

### **11.3.3. Potential Risks:**

Only minimal risks are associated with the subjective sleep measures and quality of life assessments to be administered to children or their parents. Risks associated with polysomnography are relatively small. In preparation for polysomnography, particularly for the first time, placement of the sensors can create transient discomfort or anxiety for some children, especially those with development disabilities. Other risks of the sleep studies include the stress of an unfamiliar environment, stranger anxieties, a night of sleep that may not be as restful as that obtained at home, and cutaneous allergic reaction or irritation that can occur at the site of electrode or tape placement. Finally, as in any research, risks exist for breach of confidentiality and loss of data. Overall, the benefit to the child of sleep study results, and what is almost always a fun, positive, and memorable experience is likely to outweigh potential harm. Almost all children and families (95%) who have completed similar testing protocols at baseline in the past have been happy to repeat them again.

The protocol also calls for subjects to use ssNPA therapy nightly. This requires commitment on the part of each child and parent. However, the treatment is not onerous, and in clinical settings NPA has been used in children of all ages. Our pilot data (under the UM Innovative Care Consent process) demonstrates that the treatment is safe and effective in children with a craniofacial malformation and hypotonia, however, NPA devices are not yet FDA-approved for use. In children with sleep apnea, adenotonsillectomy or use of PAP are the usual therapies and have been shown to improve quality of life. However, in children with HUAO, treatment of OSA presents an extremely difficult challenge, in part due to frequent multilevel upper airway obstruction secondary to anatomic features that can lead to diffuse, circumferential collapse. Thus, many surgical approaches, other than tracheostomy, often fail and a majority of children with HUAO have residual OSA following adenotonsillectomy. This often necessitates treatment with PAP, but the rate of adherence is low in typically developing children and even lower in those with developmental disabilities. Tracheostomy then becomes a final option.

Specific risks from using the ssNPA include blockage of the endotracheal tube with secretions.

The risks of completing validated questionnaires about sleep and quality of life are minor.

Finally, participants will reveal personal information about themselves and there is a risk of breach of confidentiality. Participants will be informed of the procedures taken to preserve confidentiality.

The proposed protocol adheres to the ethical principles outlined by the National Commission for the Protection of Human Subjects of Biomedical and Behavioral Research. Respect for persons is maintained, as the adult parent or guardian with full capacity will provide written informed

consent, a child over the age of 8 years and able to understand the study will provide written assent were appropriate, and a younger child will give verbal assent. The principle of beneficence is respected as for each participant the potential for personal benefit from this study will outweigh the small risks involved. This study will not subject any child to tests or treatments that stand no chance to benefit him or her personally. No child will be deprived of needed medical care. Agreement to participate in this research will not prevent any family from withdrawing at any time. Lastly, the principle of justice is respected because the population to be studied will be exactly that which stands to gain most from the results of the study.

